## **4 SELECTION AND ENROLLMENT OF PARTICIPANTS**

### **4.1 Study Enrollment Procedures**

#### **4.1.1 Screening**

Patients will be identified for screening via diagnosis codes for AF on chart review. This can be easily identified by querying current electronic medical record systems. If needed, patients with ICMs can be identified by lists maintained at each study center of those who undergo ICM insertion.

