#### **4.1.2 Consent and Enrollment**

Patients who meet inclusion and exclusion criteria after screening will be directly enrolled in the study. No randomization will occur, but patients will be separated into an ICM and non-ICM arm. We will enroll approximately 2500 patients [n=1250 (ICM) and n=1250 (non-ICM)] from 2018-2021. No consent will be required due to the nature of the study.

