### **4.2 Inclusion Criteria**

- Patients > 18 years of age
- Present for management of AF
- ICM is inserted at the discretion of the treating physician

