### **4.3 Exclusion Criteria**

- Patients < 18 years of age
- Presence of a permanent pacemaker, implantable cardiac defibrillator, or cardiac resynchronization therapy
- Unable to tolerate ICM or traditional monitoring with ECG, Holter, or MCOT monitoring
- Unable to tolerate AAD, OAC, and CA as part of AF standard of care
- ICM inserted for cryptogenic stroke or syncope
- Was not followed > 12 months
- CA performed for AF before ICM implant

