## 9.2 Sample Size and Randomization

We will aim for 2500 enrolled participants to result in a 99% power for statistical significance, assuming no difference in AAD, OAC, or CA use rates between those with ICM and non-ICM monitoring methods. We cannot control the exact number of subjects but will attempt a 1:1 allocation into the ICM and non-ICM arms to result in 1250 patients each.

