## 9.3 Outcomes

Primary	Secondary

• Access to care

• Time of AAD initiation

• Time of OAC initiation

• Time to CA

• Any changes or discontinuation of AAD post-ablation

• Any changes or discontinuation of OAC post-ablation

• Arrhythmia recurrence

• Redo Ablation

	

• Systemic thromboembolic events

• All AF and cardiovascular related hospitalization

• Heart failure exacerbations

• Bleeding complications

• Cardiovascular mortality

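### The prior-ablation exclusion is tied to the ICM implant, so previously ablated patients are barred from the ICM arm but remain eligible for the non-ICM arm

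*Combined protocol and SAP*

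**What the plan says.** - **Design.** Section 4.1.2: "No randomization will occur, but patients will be separated into an ICM and non-ICM arm". Section 9.2 says the team "will attempt a 1:1 allocation into the ICM and non-ICM arms to result in 1250 patients each".
- **Source of patients.** Section 4.1.1: "Patients will be identified for screening via diagnosis codes for AF on chart review". Centre lists of ICM insertions may be used in addition.
- **Inclusion (4.2).** The clinical requirement common to both arms is "Present for management of AF". Nothing there limits earlier ablation, stroke or syncope.
- **Exclusion (4.3).** Two lines refer to the device: "CA performed for AF before ICM implant" and "ICM inserted for cryptogenic stroke or syncope". No other line mentions earlier ablation, stroke or syncope.
- **Outcomes.** Section 3 makes AF freedom at 12 months, with continued AAD and OAC use, the primary outcome. Section 9.3 lists as primary, among others, time to CA, AAD and OAC changes after ablation, arrhythmia recurrence and redo ablation. "Systemic thromboembolic events" is a secondary outcome.
- **Data.** Table 1 (6.1) has fields for need for and time to CA, need for and time to redo ablation, cardioversion history, baseline AAD use and CVA/TIA. It lists no ablation before entry, no syncope and no reason for monitoring. The table is introduced as a non-exhaustive list.
- **Analysis (9.4).** t-tests, Mann-Whitney, chi-square, Cox models and Kaplan-Meier curves. No covariates, matching, weighting or stratification are named.

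**The concern.** A patient ablated for AF some years ago who later receives an ICM is excluded. The same patient, followed with ECGs, Holter or MCOT, is eligible, because there is no implant for the ablation to precede. The ICM arm is thus ablation-naive at implant, while the non-ICM arm is a mixture in unknown proportion.

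This imbalance is written into the eligibility rules, and it adds to whatever selection follows from leaving ICM insertion to the physician. Several primary outcomes depend directly on ablation history. A previously ablated patient's chance of another ablation, risk of recurrence and drug use after ablation need not match those of a naive patient. There is also a coding problem: the first in-study ablation of such a patient is clinically a repeat procedure, and the plan does not say whether it counts as CA or as redo. A difference between arms on these outcomes could therefore arise with no effect of monitoring at all.

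**Working it through.** **Step 1. Who can meet each criterion.**

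| Criterion (4.3) | Patient with an ICM | Patient without an ICM |
|---|---|---|
| AF ablation before implant | Excluded if ablated earlier | Cannot be met |
| ICM placed for cryptogenic stroke or syncope | Excluded by the reason for the device; past stroke with an ICM placed for AF stays in | Cannot be met |

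The first line sorts patients by ablation history in one arm only. The second sorts by device indication, so stroke history can be present in both arms.

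**Step 2. The plan's own figure.** Section 9.2 states: "We will aim for 2500 enrolled participants to result in a 99% power for statistical significance". No effect size or control rate is given, so the 99% cannot be reproduced. The point here does not depend on it.

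**Step 3. Hypothetical effect on CA.** From the plan: 1250 per arm and a 0.05 significance level. Assumed: no ICM effect; 12-month CA rate 40% if naive and 15% if previously ablated; share *f* of the non-ICM arm previously ablated.

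Non-ICM rate = (1 − *f*) × 0.40 + *f* × 0.15. Test: z = difference / √[p̄(1 − p̄) × 2/1250], where p̄ is the mean of the two rates.

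| *f* | ICM | Non-ICM | Difference | SE | z | Two-sided p |
|---|---|---|---|---|---|---|
| 5% | 40% | 38.75% | 1.25 points | 0.0195 | 0.64 | 0.52 |
| 15% | 40% | 36.25% | 3.75 points | 0.0194 | 1.93 | 0.054 |
| 30% | 40% | 32.50% | 7.50 points | 0.0192 | 3.90 | 0.0001 |

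These p-values are for expected rates observed exactly. Only the 30% share crosses 0.05.

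**Step 4. Coding of repeat procedures.** Expected in-study ablations among previously ablated non-ICM patients are *f* × 0.15 × 1250 = 9.4, 28.1 and 56.3. Step 3 counts them as CA, so they must not also be presented as an excess of redo procedures. If they were coded as redo only, the non-ICM CA rate would be (1 − *f*) × 40% = 38%, 34% and 28%. If previously ablated patients were left out of the denominator, it would be 40% and the gap would vanish. The plan does not say which applies.

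**Step 5. Hypothetical effect on 12-month AF freedom.** Assumed: 70% AF freedom without prior ablation, lower by a gap *g* with it, and no ICM effect. Spurious difference = *f* × *g*. The rejection probability is that of the two-sided 0.05 two-proportion test at 1250 per arm.

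| *f* | *g* | Spurious difference | Rejection probability |
|---|---|---|---|
| 0% | any | 0 | 5.0% |
| 5% | 10 points | 0.5 points | 5.9% |
| 10% | 15 points | 1.5 points | 12.8% |
| 20% | 15 points | 3.0 points | 36.5% |
| 30% | 20 points | 6.0 points | 89% |

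The documents do not fix the sign of *g* either. The first row is what an arm-neutral criterion would restore for this one source of bias.

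**Step 6. The stroke/syncope line.** Assume a 1% 12-month thromboembolic risk, an affected share of 5% to 20% in the non-ICM arm only, and a risk ratio of 2 to 3. The rejection probability is then 5.2% to 15.1%. This overstates the effect, because ICM patients with past stroke are not all excluded.

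**The case against.** The wording of the ablation line is hard to defend, but four arguments limit what follows from it.

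1. **The size is unknown.** Every share and rate above is assumed. At small shares the effect is negligible, and in the CA example even 15% falls short of significance. This stands: the documents show an asymmetry, not how large it is.
2. **Prior ablation might still be collected.** A reader might infer from its absence in Table 1 that adjustment is impossible. The documents do not support that: the table is expressly non-exhaustive and the study is a chart review, so the history may be retrievable. What stands is that neither its collection nor its use in the analysis is prespecified.
3. **The stroke/syncope line is not a history exclusion.** A reader might infer that stroke history remains in the non-ICM arm alone and inflates its thromboembolic rate. The text does not say this. It excludes by the reason for the device, the requirement to present for AF management applies to both arms, and CVA/TIA is recorded for everyone. What remains is patients whose AF was found in such a work-up and who then presented for AF management. Syncope and the reason for monitoring are not listed fields.
4. **Comparability is a wider problem.** With physician-chosen monitoring and no planned adjustment, this is one component among several. That is true, but this component is created by the protocol itself and can be removed by rewording.

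**Conclusion.** The point holds for prior ablation. Read as written, 4.3 yields an ICM arm that is ablation-naive at implant and a non-ICM arm that need not be. The difference bears on several primary outcomes, and the plan has no step that corrects it. This rests on the text alone and needs no assumption.

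The size of the bias cannot be derived from the documents. Under the assumed rates it runs from trivial (1.25 points in CA, p = 0.52, at a 5% share) to decisive (7.5 points, p = 0.0001, at 30%). For AF freedom, the false-positive rate runs from 5.9% to 89%. These figures show what could happen and are not estimates. The plan as written would not reveal which case applies, because the share is not a listed data item.

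The stroke/syncope line is a minor wording matter. It is one-sided by device indication, with a partial and possibly small imbalance.

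**What to change.** 1. **Define an index date for both arms.** The plan has none for non-ICM patients. One option is ICM implant for the ICM arm and the start of the qualifying non-ICM monitoring for the non-ICM arm. State which date applies to patients who cross over, since 9.1 allows this at any time.
2. **Make the ablation criterion arm-neutral:** 'any CA for AF before the index date', applied to all patients.
3. **Add a field to Table 1:** 'CA before index date (0/1)', so that each site can check the rule.
4. **Minor:** reword the stroke/syncope line as the reason for monitoring in both arms, and record that reason.

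If the sponsor prefers to keep previously ablated patients, the minimum alternative is to record prior ablation in both arms, prespecify adjustment or restriction, and state how a first in-study ablation in such a patient is coded.

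**Cost.** A protocol amendment, which 4.4 provides for, and one chart field for the ablation point, plus a second for the reason for monitoring. Some non-ICM patients will be lost, but that pool is drawn from AF diagnosis codes and could probably be replenished. Setting an index date for non-ICM patients takes some abstraction effort.

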## **2 BACKGROUND AND RATIONALE**

### **2.1 Background on Condition, Disease, or Other Primary Study Focus**

AF is the most frequent cardiac arrhythmia, with a global prevalence that is only expected to increase. A significant number of patients – up to 38% – may be asymptomatic, making management more difficult. [1] Regardless of symptoms, AF is associated with significant morbidities, including but not limited to heart failure, stroke, dementia, and death.

The management of AF is complex, with clinical decisions related to rate and rhythm control strategies with AADs and CA and stroke prevention. Like other chronic diseases, frequent routine assessments help select, assess, and change management strategies. Implantable cardiac monitors (ICMs) are another option that store electrocardiogram (ECG) tracings for years at a time, enabling continuous monitoring, assessment of AF burden, and therapy efficacy. Previous studies have demonstrated a threefold increase in AF detection, including asymptomatic AF in cryptogenic stroke, syncope, and after CA. using ICMs.[2-4] Their use in AF management has gained popularity for this reason.

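### Eligibility does not require AF to be documented before ICM insertion and bars only two diagnostic indications, so ICM-detected AF may enter one arm preferentially

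*Combined protocol and SAP*

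**What the plan says.** All references are to the combined protocol and SAP.

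- **4.3 Exclusion Criteria** names two ICM indications: "ICM inserted for cryptogenic stroke or syncope". A further ICM-related line, "CA performed for AF before ICM implant", concerns the order of ablation and implant. It does not concern why the device was placed.
- **4.2 Inclusion Criteria** asks that patients "Present for management of AF" and adds that "ICM is inserted at the discretion of the treating physician". It gives no standard for documenting AF, no date, and no order relative to insertion.
- **4.1.1 Screening** starts from codes: "Patients will be identified for screening via diagnosis codes for AF on chart review". If needed, "patients with ICMs can be identified by lists maintained at each study center of those who undergo ICM insertion". The code need not pre-date the device, the lists are not restricted by indication, and the list route can serve only the ICM arm.
- **6.1, Table 1** collects duration of arrhythmia in months, with no anchor date. It lists no ICM indication, insertion date or date of first AF documentation. The table is described as non-exhaustive, but nothing commits sites to these items.

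**The concern.** The comparison is meant to show what happens to AF patients managed with an ICM against those managed with ECG, Holter or MCOT. That requires AF in both arms to have been found by means that do not depend on the arm. If some ICM patients count as AF patients only because the ICM found their AF, the exposure has helped to decide who is eligible.

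Such patients may differ from clinically diagnosed ones in burden, in symptoms and in use of ablation, antiarrhythmic drugs and anticoagulation. Any such difference would appear as an effect of the monitoring method. Section 9.4 names no adjustment covariates. Even if it did, adjustment has little or no comparable non-ICM group to draw on for AF that only continuous monitoring would reveal. Eligibility is therefore the main protection, and it is silent on the order of events.

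**Working it through.** **Step 1. Can a device-first patient pass the criteria?** Take a patient whose ICM was placed for palpitations. This is my example; the documents do not name it. The device shows AF, and the patient is then coded and managed for AF.

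| Rule | Does it stop this patient? |
|---|---|
| AF diagnosis code (4.1.1) | No; the code may follow the device |
| ICM insertion list (4.1.1) | No; the list is not limited by indication |
| Presents for AF management (4.2) | Not clearly; true once AF is being managed |
| ICM at physician's discretion (4.2) | No |
| Cryptogenic stroke or syncope (4.3) | No; different indication |
| Ablation before implant (4.3) | No; none performed |

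No rule clearly excludes this patient.

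**Step 2. Is there a like patient in the other arm?** In part. AF first found on ECG, Holter or MCOT, with or without symptoms, can be coded and enter the non-ICM arm. Brief or low-burden AF that intermittent recording misses is not coded, so it is under-represented there.

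**Step 3. Size, as illustration only.** The plan's one design figure is 99% power with 2500 patients (9.2). It comes with no event rates or effect size, so it cannot be reproduced, and this point does not depend on it.

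From the documents: 1250 per arm (4.1.2, 9.2) and a significance level of 0.05 (9.4), taken as two-sided. Assumed: non-ICM 12-month rate of 60%, no true ICM effect, a share f of the ICM arm that is device-first, and an outcome gap g between those patients and the rest.

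Spurious difference: d = f × g.

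Probability that a two-proportion z-test rejects in the direction of d: Φ[(|d| − 1.96 × SE0) / SE1]. SE0 is the pooled and SE1 the unpooled standard error.

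Worked case, f = 20% and g = 20 points, ICM arm higher:
- d = 0.20 × 0.20 = 0.04, so 64% v 60%, pooled 62%.
- SE0 = √(2 × 0.62 × 0.38 / 1250) = 0.01942.
- SE1 = √((0.60 × 0.40 + 0.64 × 0.36) / 1250) = 0.01940.
- (0.04 − 1.96 × 0.01942) / 0.01940 = 0.10, and Φ(0.10) = 0.54.

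| Share f | Gap g (points) | Spurious difference (points) | Rejection, ICM arm higher | Rejection, ICM arm lower |
|---|---|---|---|---|
| 5% | 10 | 0.5 | 4.4% | 4.4% |
| 10% | 20 | 2.0 | 17.5% | 17.3% |
| 20% | 20 | 4.0 | 54.0% | 52.6% |
| 30% | 30 | 9.0 | 99.7% | 99.5% |

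These figures count rejection in the direction of the bias only; with no bias that would be 2.5%. In the first row the opposite tail adds about 1.3 points (Φ[(−0.005 − 1.96 × 0.01958) / 0.01957] = 0.013), so total rejection is about 5.7%, close to the nominal 5%. In the second row it adds about 0.1 points, and in the last two nothing visible.

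**The case against.** The best defence is that the protocol means AF first. Its objective is set in patients with AF, the main screen is an AF code, and the insertion lists are only an aid, since anyone found that way must still meet 4.2. Barring ablation before the implant presupposes AF that may precede the device, and 9.1 lets patients already on traditional monitoring cross to an ICM. Read together, these suggest a device placed to manage known AF.

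This stands as a reason to say that such patients may enter, not that they do. It does not close the gap. If presenting for AF management already removed device-first patients, the stroke and syncope line would be largely redundant. Two sites could also apply 4.2 differently in good faith.

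Four stronger readings are tempting, and the documents do not support them:

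- **That ICM-detected patients have no counterpart in the non-ICM arm.** AF first found on ECG, Holter or MCOT can enter it. The imbalance is one of degree.
- **That the threefold detection figure sizes the problem.** Section 2.1 says "Previous studies have demonstrated a threefold increase in AF detection, including asymptomatic AF", but the sentence goes on to limit this to cryptogenic stroke, syncope and the period after ablation. Section 4.3 largely removes those settings at entry, so the figure gives no size for the patients who remain.
- **That treatment-initiation times in these patients start at device detection.** The protocol defines no time origin for those outcomes, so this cannot be shown.
- **That a large false difference is likely.** The share, the gap, its direction and the base rate are all assumed. With small values the effect is negligible.

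**Conclusion.** The concern holds in limited form. As written, eligibility can depend on the exposure: two diagnostic indications are barred, others are not, and nothing fixes AF documentation before insertion. That follows from the text of 4.1.1, 4.2 and 4.3 and needs no assumption.

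The size and direction of the bias cannot be taken from the documents. Under the stated assumptions (60% base rate, no ICM effect, 1250 per arm), false significance runs from near nominal at a 0.5-point difference to about 53-54% at 4 points; the 9-point row shows only that extreme inputs give extreme results. What can be said generally is that a sample this large can make a modest selection difference look convincing. The eligibility rule should be corrected because the change is specific and cheap, not because a large bias has been shown.

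**What to change.** 1. **Section 4.2.** For both arms, require AF documented on an ECG or external monitor before the index date. Define that date as ICM insertion in the ICM arm and the start of the non-ICM monitoring strategy in the non-ICM arm. The protocol has no such date now, and the rule cannot be applied without one.
2. **Section 4.3.** Replace the stroke and syncope line with: *ICM inserted for any reason other than management of already documented AF*.
3. **Table 1.** Add ICM indication, ICM insertion date and date of first AF documentation.
4. **If charts are already abstracted.** Run a sensitivity analysis that excludes patients whose first AF record came from the ICM. This also needs the source and date of that first record.

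Cost: two eligibility lines, an index-date definition and a few more chart fields. Some ICM patients will become ineligible; the documents do not allow an estimate of how many.

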## **5 STUDY INTERVENTIONS**

### **5.1 Interventions, Administration, and Duration**

No intervention or administration will be performed due to the observational nature of each phase. Charts of patients enrolled in the study will be reviewed for an initial monitoring method, any changes in

management, including AAD, OAC, CA, as per physicians' preference, arrhythmia recurrence, need for redo CA, and AF-related complication, for 12 months after enrollment. Lastly, the primary outcomes of AF freedom and continued AAD and OAC use will be noted at the end of the study duration.

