## 6.3 Follow-up Visits

Follow-up will occur up to 12 months after enrollment into the study. Follow-up visits and management changes will occur at the treating physician's discretion.

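### Section 4.3 admits only patients followed for more than 12 months, so cohort entry depends on later retention and, depending on an unstated death rule, on later survival

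*Combined protocol and SAP*

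**What the plan says.** All references are to the combined protocol and SAP.

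- **Section 4.3 (exclusions):** "Was not followed > 12 months". No start date is given for the 12 months, and nothing is said about patients who die.
- **Section 4.1.2:** "Patients who meet inclusion and exclusion criteria after screening will be directly enrolled in the study". The exclusion therefore acts before entry. Section 3 makes the study retrospective, so each patient's later follow-up is already on record at selection.
- **Section 5.1:** enrolled patients' charts are reviewed for outcomes including "arrhythmia recurrence, need for redo CA, and AF-related complication, for 12 months after enrollment".
- **Section 6.3:** "Follow-up will occur up to 12 months after enrollment into the study".
- **Section 9.3:** one of five secondary outcomes is "Cardiovascular mortality", with no time window.
- **Section 1.1:** the primary objective refers to AF freedom and drug use after ICM implantation. Section 9.1 lets patients cross to ICM at any time, so implantation can fall later than enrollment.
- **Section 9.4:** Cox models and Kaplan-Meier graphs are planned, with no rule for censoring, death or loss to follow-up.
- **Table 1 (Section 6.1):** shows no field for death, cause of death or last contact. The list is expressly open-ended, so this is supporting evidence only.

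**The concern.** Eligibility is decided by something that happens after baseline. A patient who left care at month 4 is removed from every outcome, including any stroke, bleed or hospitalization recorded before leaving. If death ends follow-up for the purpose of this rule, a patient who died at month 4 is removed too, and the fatal event with them. The protocol's own background says "AF is associated with significant morbidities, including but not limited to heart failure, stroke, dementia, and death", so deaths are to be expected in this population.

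Two things are at stake. First, on one reading the mortality outcome has no events in either arm whatever the data, and an empty comparison could be misread as no difference. Second, on any death rule, AF freedom, continued OAC and AAD use and all the other comparisons describe only those who stayed in care. Arm membership is at the physician's discretion (Section 4.2) and so are follow-up visits (Section 6.3), so retention could differ by arm. No exit figures are given. Section 5.1 reviews charts of enrolled patients only, and no section plans to report those who exit.

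**Working it through.** The plan gives no mortality, attrition or event rate, so it has no figure of its own to reproduce. From the documents: 1250 patients per arm and 2500 in total (Sections 4.1.2, 9.2), a 0.05 significance level (Section 9.4), follow-up required beyond 12 months (Section 4.3), and an outcome window of at most 12 months after enrollment (Sections 5.1, 6.3). Every other input is assumed for illustration.

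**Step 1. When is the mortality outcome empty?** Three conditions together are sufficient:

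1. the follow-up clock starts at enrollment or later (a later implant date has the same effect);
2. a patient who dies counts as not followed;
3. cardiovascular deaths are counted only within 12 months of enrollment.

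An included patient must then outlive the outcome window, so the count is 0 v 0. If condition 2 fails, all deaths remain. If condition 1 fails, some may remain.

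**Step 2. Deaths countable per arm.** Assume one-year cardiovascular mortality m of 1% or 2% and a constant hazard h = -ln(1 - m). If death counts as not followed and the follow-up clock starts d months before the outcome clock, only deaths in the last d of the 12 months are kept: 1250 × (1 - exp(-h·d/12)).

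| Reading | m = 1% | m = 2% |
|---|---|---|
| d = 0 (three conditions hold) | 0 | 0 |
| d = 3 | 3.1 | 6.3 |
| d = 6 | 6.3 | 12.6 |
| d = 12, or death counts as complete follow-up | 12.5 | 25 |

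With conditions 1 and 2, retaining 2500 patients at an assumed all-cause mortality of 2% or 4% means removing 2500m/(1 - m) = 51 or 104 deaths.

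**Step 3. Selection on retention.** Let R be the true 12-month risk, equal in both arms (true RR 1.00). Let L be the fraction excluded for short follow-up and k the exclusion probability with an event relative to without. The exclusion probability without an event is x = L/(kR + 1 - R). The risk among those retained is R(1 - kx)/(1 - L).

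Example: R = 0.10, k = 3.
- ICM, L = 0.05: x = 0.05/1.2 = 0.0417; retained risk 0.10 × (1 - 0.125)/0.95 = 0.0921.
- Non-ICM, L = 0.15: x = 0.15/1.2 = 0.125; retained risk 0.10 × (1 - 0.375)/0.85 = 0.0735.
- RR = 0.0921/0.0735 = 1.25.

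The table gives the RR (ICM v non-ICM), with the chance of p < 0.05 in brackets (two-sided two-proportion test, 1250 retained per arm).

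| Excluded, ICM v non-ICM | R | k = 0.5 | k = 1 | k = 2 | k = 3 |
|---|---|---|---|---|---|
| 5% v 15% | 10% | 0.95 (8%) | 1.00 (5%) | 1.12 (14%) | 1.25 (39%) |
| 5% v 15% | 30% | 0.95 (13%) | 1.00 (5%) | 1.07 (20%) | 1.13 (45%) |
| 5% v 10% | 10% | 0.97 (6%) | 1.00 (5%) | 1.05 (7%) | 1.11 (12%) |
| 5% v 10% | 30% | 0.98 (7%) | 1.00 (5%) | 1.03 (8%) | 1.06 (14%) |
| 15% v 5% | 10% | 1.06 | 1.00 | 0.89 | 0.80 |
| 15% v 5% | 30% | 1.05 | 1.00 | 0.93 | 0.89 |

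Equal exclusion with equal k gives RR 1.00. Equal exclusion of 10% with k = 1 in the ICM arm and k = 2 in the non-ICM arm gives 1.10 (R = 10%) and 1.06 (R = 30%). Equal exit rates therefore do not by themselves rule out bias.

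**The case against.** The strongest reply is that this is a missing definition that one sentence would cure. Listing cardiovascular mortality suggests that the authors meant deaths to count, and it is one of five secondary outcomes, not the primary. That stands as far as mortality goes. A reader might infer that the plan makes cardiovascular mortality 0 v 0. The documents do not support that: enrollment is the natural origin but Section 1.1 points also to implantation, no section classifies deaths, and Section 9.3 sets no window, although Section 6.3 supports 12 months.

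A second reply is that bias between arms is not shown. That also stands. The extreme ratios need a threefold exclusion gap and k = 3. With 5% v 10% excluded, the chance of a false positive is 5% to 14%, against 5% with no bias.

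A third is that AF freedom at 12 months (Section 3) needs 12-month ascertainment, so dropping the exclusion changes that analysis little. This is partly right: status at 12 months will still be reported among those assessed. But that is a missing-data problem for one type of outcome. It is no reason to remove patients from every outcome, and the planned Cox and Kaplan-Meier methods accept partial follow-up.

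What survives all three is that the written rule drops early leavers even once deaths are clarified. The only exception is a follow-up clock that starts a full year before the outcome clock.

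**Conclusion.** The point holds as a flaw in a stated rule, not only as missing detail. Selection on later retention follows from Sections 4.3, 4.1.2, 5.1 and 6.3, with the one-year-earlier clock as the only escape. Selection on survival follows only if death counts as not followed. An empty mortality comparison needs the three conditions in Step 1, and the listing of mortality suggests it was not intended.

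A reader might also infer that the ICM comparison is biased in a known direction. It is not: bias requires exit, or the prognosis of those who exit, to differ by arm, and the documents neither show nor exclude this. The illustrative range of 0.80 to 1.25 rests wholly on assumed inputs, includes 1.00, and is not a bound. This should be fixed before charts are selected, but it has not been shown to invalidate the study.

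**What to change.** 1. Define one index date that applies to both arms, and start the eligibility and outcome clocks there.
2. Replace the follow-up exclusion with inclusion of all patients eligible at the index date, followed to the earliest of 12 months, death or last contact.
3. Add index date, death date, cause of death and last-contact date to Table 1.
4. Analyse time-to-event outcomes with the planned Cox and Kaplan-Meier methods, censoring at last contact. Treat non-cardiovascular death as a competing event for cardiovascular mortality. Competing-risk methods for non-fatal outcomes are optional: with an assumed 4% deaths and constant hazards, one minus Kaplan-Meier gives 10.0% against a cumulative incidence of 9.8%, and 30.0% against 29.4%.
5. Report 12-month AF freedom and OAC/AAD status among those alive and assessed, with a missing-data sensitivity analysis.
6. Report early exits by arm and reason, and keep the complete-12-month cohort as a sensitivity analysis. Exits can be found through the record query in Section 4.1.1: "Patients will be identified for screening via diagnosis codes for AF on chart review".

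**Minimum if the exclusion is kept:** state its time origin and that death counts as complete follow-up. This removes the 0 v 0 problem but not the selection on staying in care.

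**Cost:** one eligibility line, an index-date definition, four chart fields and analysis wording. Some patients will have partial follow-up and missing 12-month status. Censoring assumes non-informative loss, which the exit table can check only in part. Extra charts arise only if 2500 completers are still wanted: 2500L/(1 - L) = 132, 278 or 441 at an assumed 5%, 10% or 15% excluded. If about 2500 are enrolled in total, none need be added.
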